11.8.3 Categorical Variables

- For categorical variables, summary statistics will include counts and percentages. Confidence limits for binary variables will be computed using the exact binomial distribution.
- Categorical variables will be compared by Fisher's exact test.

11.8.4 Non-Inferiority Analyses

- Non-inferiority tests at a point in time are based on the rate difference approach.
- The test is performed at a point in time T , using the Kaplan-Meier estimates for freedom from the endpoint being evaluated, and the Greenwood standard errors for these estimates. The test will be performed by computing the two-sided 95% confidence limit for the event rate difference (TAVR - SAVR). The acceptance criterion is that the upper confidence limit is less than Delta, where Delta is the predetermined non-inferiority margin of 6.0%.
- In analysis of the primary endpoint, there will be little or no censored data. The only censoring would be due to lost to follow-up or withdrawal from the trial.
- It is conceivable that there will be no censored data at all in evaluating the primary endpoint. In such a case the Kaplan-Meier estimators are pure proportions, and the Greenwood variance is the standard variance for an estimated proportion. The confidence limits would agree with those produced by

standard frequency analysis.

- For the primary endpoint in this trial the non-inferiority margin of 6.0% has been chosen.

11.8.5 Missing Data

- Missing variables will not be imputed for planned analyses, except where otherwise specified.
- The primary safety and effectiveness endpoint will be based on Kaplan-Meier estimates, which automatically account for censored data.
- For sensitivity purposes, tipping point analyses for the primary endpoints are defined in the SAP.
- Tipping point analysis will also be presented for the secondary endpoint involving KCCQ.

11.8.6 Multiple comparisons

A formal multiple comparisons analysis is presented in section 11.5 for the named secondary endpoints for labeling purposes. In all other cases p-values will be presented as computed, without any adjustments for the comparisons.

11.8.7 Adverse event analysis

- Adverse event analysis will involve both site and CEC reporting.
 - Where events have been adjudicated by the CEC, those adjudications will be used in preference to site reports.
 - Where site events are analyzed, the MedDRA coding will be used. The underlying site evaluations will not be used for analysis, but may appear in listings as appropriate.
- Adverse events to be analyzed include the composites involved in the primary and secondary endpoints, as well as all events contained in these composites. All events adjudicated by the CEC will also be analyzed.
- Adverse event tables will present data at 30 days, 6 months, and 1 year. The tables will include counts of events, patients with event, and Kaplan-Meier event rates at the specific time point. The trial arms will be compared by the log-rank test
- Late adverse events (> 30 days) will be analyzed by a constant hazard model, and upper one-sided confidence limits will be given for the rates.

- Adverse event data past 1 year will be presented as counts of events and patients with event. No formal analyses will be performed for such data.

11.8.8 Periodic analyses

Periodic analyses will be performed during the trial to the extent required by the appropriate regulatory authorities and the DSMB. The sample size and endpoint timing for this trial is fixed in advance, and not based on these periodic analyses. Accordingly, there is no adjustment to alpha.

Other than the required reports mentioned in the previous paragraph, there will be no reporting of trial outcome data prior to the 1-year analysis close date.

It is anticipated that reporting will continue throughout the trial, with formal reports based on analysis close dates at annual intervals.

11.8.9 Quality of life questionnaires

Quality of life questionnaires will be scored according to algorithms provided by the vendor. The various summary scores produced by the algorithms will be analyzed as continuous variables.

11.8.10 General Specifications

- Trial arm comparisons will be presented wherever meaningful. *P*-values will be computed using a null hypothesis of no difference.
- Unless otherwise specified, Wald *p*-values will be presented.
- Unless otherwise specified, confidence limits and hypotheses tests will be two sided, using alpha = 0.05.
- Unless otherwise specified, the precise form of each algorithm will be the default of SAS, using the latest release installed at Edwards at the time of analysis. This will be version 9.3 or later.
- Various CRFs will contain comment fields. Data in these fields will not be analyzed, but listings will be provided for internal use on request.

11.9 CT Sub-Study

The purposes of the study are to:

1. Investigate the prevalence of the imaging abnormality.

The prevalence data come in two forms. A Yes/No value, which will be analyzed as a binary variable. A grading, which will be analyzed as an ordinal variable.

2. Investigate the relationship between the imaging abnormality and patient, procedural and pharmacology factors.

The Yes/No value will be the dependent variable in logistic regression models, with the independent variables chosen based on potential clinical relevance.

Multivariable models will be developed if the univariate analyses so suggest.

3. Investigate the relationship between imaging abnormalities and clinical events.

The clinical events to be considered will include stroke, TIA, and death. These will be modeled as time-dependent variables using proportional hazards regression, with the Yes/No value of the imaging abnormality as an independent variable.

Key echo parameters (valve area, mean gradient, and AR) will be modeled, with the Yes/No value of the imaging abnormality as an independent variable.

This sub-study analysis is unpowered.

The choice of variables for items 2 and 3 will be based on the tables presented in the papers of Makkar [26] and Pache [27].

It should be noted that the prior studies found few statistically significant baseline predictors of the imaging abnormality, and they found only minor clinical impact resulting from the abnormality. There is no reason to expect any different results in this sub-study.

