4.0 ENROLLMENT

Up to 1182 qualified patients will be randomized at up to 65 actively enrolling sites in the US. It is anticipated that approximately 5-10 sites may be selected outside of the US. Further, up to ten (10) separate US sites from targeted geographic areas will be selected to enroll patients in a single-arm registry for underrepresented populations. No site will be allowed to enroll more than 15% of patients. Edwards will notify investigative sites of enrollment closure.

Sub-studies

Of the 1182 patients, a subset of patients will also be enrolled in the following randomized sub-studies:

- CT sub-study (up to 440)
- Actigraphy/QOL sub-study (up to 400) [Enrollment Closed]

Registries

Additional patients will be enrolled in the following single-arm registries:

- Alternative Access Registry (100) [Enrollment Closed]
- Bicuspid Registry (up to 75)
- Underrepresented Populations Registry (up to 100)

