11.8 General Statistical Methodology

11.8.1 Time Dependent Variables

Time-dependent variables will be analyzed using the Kaplan-Meier algorithm, with standard errors computed by Greenwood's formula. The number of patients-at-risk will be computed at exact time points, without reference to any nominal follow-up windows. The log-rank statistic will be used for any comparison among groups.

Thirty day analysis will present both pure frequency and Kaplan-Meier rates; for later analyses only Kaplan-Meier rates will be presented. Kaplan-Meier rates will be presented at 30 days and 1 year as well as other time points as appropriate.

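### The CT sub-study's Cox models name no test, and the plan's Wald default breaks down if all of a few events fall in one imaging group; one sentence in section 11.9 would fix it

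*Combined protocol and SAP*

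**What the plan says.** Section 11.9 item 3 takes stroke, TIA and death as outcomes and asks how each relates to the imaging abnormality. Its modelling sentence reads: "These will be modeled as time-dependent variables using proportional hazards regression, with the Yes/No value of the imaging abnormality as an independent variable". It does not say which test or interval will be reported, and it has no rule for sparse events. It states that the sub-study is unpowered.

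Three general rules could fill the gap:

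- Section 11.8.10, p-values: "Unless otherwise specified, Wald *p*-values will be presented".
- Section 11.8.10, estimation: "Unless otherwise specified, the precise form of each algorithm will be the default of SAS". For Cox regression this means unpenalised partial likelihood.
- Section 11.8.1, on time-dependent variables: "The log-rank statistic will be used for any comparison among groups".

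Section 11.8.10 also sets the level: "Unless otherwise specified, confidence limits and hypotheses tests will be two sided, using alpha = 0.05". Section 4.0 gives the size: "CT sub-study (up to 440" patients. No event count, event rate or prevalence of the abnormality is given for the sub-study.

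**The concern.** A Cox model with one binary covariate has no finite estimate when every event falls in one group. The fitted log hazard ratio drifts outward until the software stops, and its standard error grows much faster. The Wald statistic, estimate over standard error, then goes to zero. The Wald p-value goes to about 1 at the point where the separation between the groups is complete.

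Objective 3 of the sub-study (section 1.3.1) is the link between the abnormality and clinical events. If the few strokes or TIAs all occurred in patients with abnormal leaflets, a report that followed the Wald default would show p of about 0.99 and an interval from zero to infinity. Section 11.9 already says that no different results are expected from earlier studies that found only minor clinical impact, so such a p-value could be taken as confirmation.

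**Working it through.** The plan states no figure on this point to reproduce, so the check is an illustration on assumed counts.

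**Inputs.** Assumed: 400 evaluable patients (the cap is 440), 60 with the abnormality (15%), 4 events, no ties, no censoring between events. From the plan: one Yes/No covariate, two-sided 0.05.

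**All 4 events in the abnormal group.** The numbers at risk at the four events are 400, 399, 398, 397 in total, of whom 60, 59, 58, 57 are abnormal and 340 normal each time.

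- *Wald.* For large β the information is about e^(−β) × (340/60 + 340/59 + 340/58 + 340/57) = 23.26 e^(−β), so the standard error grows as e^(β/2). Newton iteration with a relative-gradient stop of 1e-8 ends at β = 18.8, SE about 2,500. Then z = 18.8/2,500 = 0.0075 and p = 0.994. The 95% interval for the hazard ratio runs from effectively 0 to infinity.
- *Likelihood ratio.* As β goes to infinity the statistic tends to 2 × [ln(400/60) + ln(399/59) + ln(398/58) + ln(397/57)] = 2 × (1.897 + 1.911 + 1.926 + 1.941) = 15.35, p = 0.00009.
- *Fisher exact.* (60 × 59 × 58 × 57)/(400 × 399 × 398 × 397) = 0.00046.
- *Log-rank (score).* Observed minus expected = 4 − (60/400 + 59/399 + 58/398 + 57/397) = 4 − 0.587 = 3.413. The variance is 0.501. Chi-square = 3.413²/0.501 = 23.25, p = 1.4e-6. This does not fail, but it is far smaller than the exact value.
- *Profile-likelihood interval.* Solving 2 Σ ln[(a + 340/HR)/a] = 3.84 over a = 60, 59, 58, 57 gives a lower limit of HR = 9.4 and no upper limit. So the data do support a usable bound.

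**Other splits, same assumptions.**

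| Events abnormal/normal | Wald p | Fisher p |
|---|---|---|
| 2/2 | 0.079 | 0.109 |
| 3/1 | 0.013 | 0.012 |
| 4/0 | 0.994 | 0.0005 |
| 0/4 | 0.995 | 1.0 |

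Wald tracks the exact test until separation is complete. For 0/4 the likelihood-ratio statistic is 2 × [ln(400/340) + ln(399/339) + ln(398/338) + ln(397/337)] = 1.31, p = 0.25. No test is significant, but the fitted hazard ratio is near 0 with a Wald interval from 0 to infinity. The profile upper limit, from 2 Σ ln[(60 HR + b)/b] = 3.84 over b = 340, 339, 338, 337, is 3.5.

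**Wider range.** With N = 440, prevalence 5% to 30% and 2 to 10 events all in the abnormal group, the Wald p was 0.992 to 0.999 throughout. The exact value depends on the stopping rule: at 10% prevalence and 5 events it was 0.96 at 1e-6 and 0.9999 at 1e-12, never near significance.

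**How often.** With prevalence q and hazard ratio h, each event falls in the abnormal group with probability π = qh/(qh + 1 − q), ignoring depletion of the risk set. All D events do so with probability π^D, and all fall in the normal group with probability (1 − π)^D. At q = 0.15:

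| True hazard ratio | π | All abnormal, D = 2 / 3 / 4 | All normal, D = 2 / 3 / 4 |
|---|---|---|---|
| 1 | 0.150 | 2.3% / 0.3% / 0.05% | 72% / 61% / 52% |
| 5 | 0.75/1.60 = 0.469 | 22% / 10% / 5% | 28% / 15% / 8% |
| 10 | 1.50/2.35 = 0.638 | 41% / 26% / 17% | 13% / 5% / 2% |

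All-normal is the more common direction up to a hazard ratio of 5; at 10 the order reverses.

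**The case against.** **The log-rank rule.** Section 11.8.1 applies the log-rank test to any comparison among groups on time-dependent variables. Section 11.9 item 3 uses that same term for these outcomes and compares two groups. Section 11.8.10 imposes Wald only where nothing else is specified. A reader might infer that the plan commits itself to the Wald p-value and would lose a signal. The documents do not establish that: they leave two readings open. What remains is that the two readings can differ as 0.994 against 1.4e-6 on the same data, that log-rank supplies no hazard ratio or interval, and that its p-value is too small at such counts.

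**Frequency.** A reader might pool the two directions and infer that these models would usually hide something. With no association and 4 events at 15% prevalence, 0.85^4 = 0.522 is the normal-group direction and 0.15^4 = 0.0005 the abnormal-group direction. Nearly all of the pooled chance is the case where no signal is masked.

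**Few events is assumed.** The 30-day rates of the intermediate-risk S3i cohort (section 1.2.2: stroke 2.60%, death 1.1%, TIA 0.37%) would give about 11, 5 and 2 events per 440. Complete separation with 8 or more events is unlikely unless the hazard ratio is very large: at 20% prevalence and hazard ratio 5 it is about 1%. On the other side, this trial enrols lower-risk patients, and anyone who dies before the 30-day sub-study scan has no imaging value. Section 11.9 gives no follow-up horizon, so the counts cannot be settled from the documents.

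**Consequence.** The sub-study is unpowered, its p-values are unadjusted, and it lies outside the labeling sequence of section 11.5. That stands, and it limits the weight of the point.

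**Conclusion.** The point holds as a cheap improvement. Section 11.9 item 3 leaves the test unnamed, and one of the two defaults that could apply gives a p-value of about 0.99 when all of a few events fall in the abnormal group. With 2 to 4 events at 15% prevalence, the chance of that is 22% to 5% at a true hazard ratio of 5 and 41% to 17% at 10. These figures rest on assumed counts and prevalence.

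When all events fall in the normal group, the significance conclusion is unchanged at these counts. It could change only with more events and higher prevalence: at 30% and 10 events, Fisher gives 0.037 against Wald 0.993. In either direction the hazard ratio and Wald interval are unusable, whichever test is chosen.

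A reader might also infer that Wald p-values rise generally as evidence strengthens. They do not; the failure is confined to complete separation. Nothing here touches the primary endpoint or the labeling tests.

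**What to change.** In section 11.9 item 3, state that:

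- p-values come from the likelihood-ratio test, Firth-penalised when all events fall in one group;
- confidence intervals are profile-likelihood, in place of Wald;
- this takes precedence over sections 11.8.1 and 11.8.10 for these models;
- event counts by imaging status are shown next to each estimate.

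The same wording may be used for the item 2 logistic models, which can meet the same problem when a factor level has only normal or only abnormal valves; no calculation was made for those.

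The cost is a few lines of SAP text and standard SAS options, with no new data. The downside is that Firth estimates are shrunk slightly toward no effect.

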12.0 STUDY ADMINISTRATION

12.1 General Study Organization

Edwards Lifesciences is the Study Sponsor and has the overall responsibility for the conduct of the study, including assurance that the study meets the regulatory requirements of the appropriate regulatory bodies.

Edwards Lifesciences will be responsible for obtaining IDE approval for the study, selecting investigators, ensuring that sites have IRB/EC approval prior to investigational device shipment, and conducting clinical site monitoring to ensure that patients are being properly consented and the study is being conducted according to the protocol.

As appropriate, Edwards Lifesciences will submit changes in the Investigational Plan to the FDA and Investigators to obtain IRB/EC re-approval.

Edwards Lifesciences will maintain copies of correspondence, data, shipment of devices, adverse device effects and other records related to the clinical trial as appropriate.

Edwards Lifesciences will submit all reports required by the FDA as identified in 21 Code of Federal Regulations (CFR) 812.150(B). This includes UADEs, withdrawal of IRB/EC approval, current investigators list, annual progress reports, recall information, final reports and protocol violations.

12.2 Data Safety Monitoring Board (DSMB)

A Data Safety Monitoring Board (DSMB) will monitor all AEs and SAEs to provide safety oversight. DSMB members will not be involved in the study and have no conflict of interest. At least one member will be a cardiothoracic surgeon with specific expertise in aortic stenosis. DSMB activities, including stopping rules for early termination, will be defined in the DSMB Charter.

12.3 Clinical Event Adjudication Committee (CEC)

The Clinical Events Committee (CEC) will adjudicate endpoint events and provide assessment of SAEs and device/procedure relatedness from enrollment through the primary endpoint. The CEC will include cardiologists and cardiothoracic surgeons with experience in the field of aortic stenosis who are not involved in the study and have no conflict of interest. CEC activities will be defined in the CEC Charter.

12.4 Study Procedures

12.4.1 Echocardiogram

Study patients will receive an echocardiogram at the visits specified in section 8.0. A central imaging core lab will be established to independently review and analyze echocardiographic images. A standardized protocol for acquiring images will be developed by the core lab and be provided to the clinical sites prior to study initiation. Sites will be trained on acquiring images prior to study initiation. Appendix J includes the echocardiogram manual of operations.

12.4.2 Computed Tomography (CT)

All study patients will have a screening CT as referenced in section 8.0. Sites will be trained on acquiring images prior to study initiation. In addition, all Screening CTs will be independently analyzed with regards to annular measurements by a CT/angiographic core lab. Appendix K-1 includes CT acquisition information.

12.4.2.1 CT Sub-Study

Study patients enrolled in the CT sub-study will have a 4D CT at visits specified in section

8.1. A central imaging core lab will independently review sub-study CTs. Appendix K-2 includes the sub-study CT acquisition information.

Investigational sites will be blinded to the resulting images unless specific clinical or echo abnormalities are present.

If any of the following events occur, a repeat 4D CT will be mandated unless the event occurs within 24 hrs of the 30 day CT; in which case the CT will be unblinded.

:

- Any neurological event
- Any potential embolic event
- Myocardial infarction
- A change in echo parameters including an increase in mean gradient of 10-20 mm Hg or a change in DVI of 0.05 - 0.1

Patients whose initial imaging data are determined to be unevaluable will not undergo subsequent imaging.

12.4.3 Quality of Life Questionnaires

Investigational sites will be provided with paper QoL questionnaires (KCCQ, EQ-5D-5L, and the SF-36). Patient questionnaires will be IRB approved prior to patient administration.

Investigational staff will administer patient questionnaires to study patients. Patients will be instructed to complete each questionnaire at visits specified in section 8.0. The patient will be instructed by the investigational staff to sign and date the paper questionnaire once the questionnaire is completed. Patients will be instructed by the investigational staff not to change questionnaire answers once the questionnaire has been completed. Investigational sites should retain the completed questionnaire in the patients' source documents. Site staff will enter data collected from the completed patient questionnaire into the EDC.

The patient level summary scores will be computed by the Edwards Biostatistics group, and these scores will be used in evaluating protocol endpoints. A QoL core lab may prepare reports of additional analyses.

Quality of life will be measured through standard surveys:

- 1) The Kansas City Cardiomyopathy Questionnaire (KCCQ) is an assessment of disability and quality of life impairment due to congestive heart failure.
- 2) EQ-5D-5L is a standardized questionnaire for describing and valuing patients' health-related quality of life for clinical and economic appraisal.

- 3) The SF- 36 is a generic health status instrument and rating scale that allows mapping of health status to population-level utility weights. This is an important metric for cost- effectiveness analysis.

12.4.4 Image Management

A central image management lab will be established to receive, maintain, and provide cardiac images (echocardiogram and CT) to the appropriate core lab for analyzing.

Instructions for image upload will be provided to investigative staff prior to study initiation. Investigative staff should upload all images to the image management core lab within 5 business days of data collection.

12.4.5 Histopathology

Histopathology studies of explanted valves will be performed. Explants will be appropriately prepared and preserved and sent to the independent histopathology laboratory for macroscopic and microscopic analysis. Investigational valves that are removed at any time with an allegation of device malfunction should be returned to the Sponsor for evaluation. All other explants (those not with an allegation of device malfunction) should be sent to the Histopathology Core Lab. Appendix L contains a complete explant protocol which includes detailed procedures for the histopathology studies.

Gross pathological examination of the entire valve and the support structure (i.e., and shape, if occurrence of intravascular trauma, tissue abrasion, uniformity of the frame, position the natural valve cusps) will be assessed.

The valves will be assessed for cusp excursion and the presence of leaflet fenestrations, rigidity tears, hematoma, thrombi and calcified nodules, cell proliferation tissue overgrowth,

fibrous sheath, and local inflammatory reaction. (One half of each leaflet must be used for the quantitative determination of inorganic calcium and phosphate).

12.5 Training

To ensure proper device usage, uniform data collection, and protocol compliance, training is required for relevant study site personnel in accordance to roles outlined in the Delegation of Authority (DoA).

At the beginning of the study, Edwards Lifesciences will provide training to site personnel. Training will include review of the instructions for use of the device, study protocol, case review process, identification of eligible patients, instructions on in-hospital data collection, standardized data collection for core laboratory analysis,

methods for soliciting data from alternative sources, and regulatory requirements.

Documentation of site personnel qualification and training should be maintained in the site's clinical trial files and copies collected and forwarded for the Sponsor site file.

Ongoing training may be provided in one of the following formats by the Sponsor or its designee: live training sessions, teleconference, WebEx, online, or read and review. The Sponsor reserves the right to enforce retraining for sites who have demonstrated study or implant procedure compliance issues.

